2.2.2 Secondary endpoints

- Predictive value of genomic events in determining mTOR inhibitor efficacy where genomic events are defined as mutations, amplifications, gains, and losses.
- Predictive value of protein biomarkers (pTEN, AKT, pSRB, LKB1) in determining mTOR inhibitor efficacy.
- Molecular landscape of endocrine-resistant disease, in particular correlations between genomic events observed

3 General statistical methods and analysis population definition

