4.1.2 Baseline characteristics

The following data will be presented for the global population and for the efficacy population.

Baseline evaluation

- Demographic data: sex, age
- Vital signs : height, weight, ECOG performance status, pulse, O₂ saturation, body temperature, and dystolic/systolic blood pressure
- Genetic mutations: BRCA1, BRCA2

History of disease

- Delay between date of diagnosis and date of inclusion
- Delay between date of disease diagnosis and date of diagnosis of the metastatic disease (or advanced disease if not metastatic)
- Delay between date of the last disease progression before inclusion and date of inclusion
- Clinical characteristics: tumor form, laterality, clinical size, TNM staging, and SBR
- Pathological examinations: pathological tumor size, histological tumor size, number of nodes involved and removed,
- Hormonal receptors status: estrogen, progesterone, androgen, IHC, amplification (if IHC 2+)
- Metastatic site at inclusion

History of treatment

- Neoadjuvant treatment (hormone therapy, chemotherapy)
- Adjuvant treatment (hormone therapy, chemotherapy)
- Radiotherapy
- Surgery
- Other

Significant medical and surgical history

The symptoms present at inclusion will be described in terms of:

• Number of patients with at least one symptom

• Number of patients with at least one grade \geq 2 symptom

Protein expression study: immunohistochemistry

Immunohistochemical staining will be performed on FFPE biopsy samples. The frequencies and other characteristics of positive tumor markers (P4EBP1, PTEN, pAKT, pS6RB, LKB1) will be presented.

The ALLRED score will be calculated as follows:

- < 10% : score 0 + intensity value (0 to 3)

- 10-30%: score 1 + intensity value (1 to 3)
- 30-50%: score 2 + intensity value (1 to 3)
- 50-70%: score 3 + intensity value (1 to 3)
- 70%-100%: score 4 + intensity value (1 to 3)

The ALLRED score is between 0 and 7.

Laboratory tests

- Complete blood count (CBC): hemoglobin, platelets, leucocytes, and neutrophils
- Coagulation: prothrombin time, partial thromboplastin time, and international normalized ratio
- Blood electrolytes: calcium and phosphorus
- Kidney function: creatinine and creatinine clearance
- Liver and pancreas function: AST, ALT, total bilirubin

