- (1) if a progression is recorded in the tumor evaluation form and if the duration between treatment initiation (everolimus) and the first documented progression is ≤7 months, then the variable "clinical benefit rate at 6 months" will be set to "no"
- (2) if condition (1) is not fulfilled and a complete response, a partial response or a stable disease is recorded in the tumor evaluation form, and if the duration between treatment initiation (everolimus) and the tumor evaluation form is ≥5 months, then the variable "clinical benefit rate at 6 months" will be set to "yes"
- (3) if condition (2) is not fulfilled and if we have no tumor evaluation between 5 and 7 months after treatment initiation and patient is non progressive or without tumor evaluation before 5 months but progressive after 7 months, or non-progressive in last evaluation occurring within 5 months then the primary endpoint "clinical benefit rate at 6 months" will be defined patient by patient during blind review but blinded to p4EBP1 level.
- (4) if condition (3) is not fulfilled and if the patient died before 7 months from other cause than clinical progression, then the variable "clinical benefit rate at 6 months" will be set to "Not Available".

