4.2.2 Secondary endpoints

- **Progression-free survival (PFS)** will be measured from the date of treatment initiation to the date of event defined as the first documented disease progression or death from any cause. Patients with no event at the time of analysis will be censored at the date of last adequate tumor assessment. The date of first progression will be determined using data from the tumor evaluation form.
- **Overall survival (OS)** will be measured from the date of treatment initiation to the date of death from any cause. Patients who are alive at the time of analysis will be censored at the date of last contact. Number of patients deceased and cause of death will be reported.

PFS and OS will be estimated using the Kaplan-Meier method. Survival curves will be plotting according to p4EBP1 (high vs low) and compared using a logrank test.

A Cox proportional hazards model will be performed to explain the progression-free survival time. Variables sufficiently informed (less than 10% missing values) and significant at a 15% level in a univariate approach will be included in a backward selection procedure to keep factors significant at a 5% level in the final multivariate model. Hazard ratios (HRs) will be presented with their 95% confidence intervals (CI).

- The clinical benefit rate at 6 months will be described with its 95% confidence interval according to:
 - the presence/absence of each studied genomic event
 - the expression levels of each studied proteomic biomarker (cutoff will be defined in the same way as mentioned for the primary endpoint)
- Descriptive statistics will be used to **characterize the molecular landscape** of endocrine-resistant disease in terms of genomic events observed. Correlations between the different types of genomic events will be studied.

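### The review that settles unclear 6-month outcomes names only p4EBP1 as masked, although the same outcome is later described by genomic events and the other protein markers

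*SAP*

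**What the plan says.** SAP section 4.2.1 derives CBR-6m by four ordered rules. Rules (1), (2) and (4) follow recorded events and dates. Rule (3) covers cases that rule (2) leaves open, beginning with the situation "if we have no tumor evaluation between 5 and 7 months after treatment initiation and patient is non progressive". For these cases the outcome "will be defined patient by patient during blind review but blinded to p4EBP1 level". No criterion for choosing yes or no is given, and the term blind review is not defined anywhere else in the SAP.

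Section 2.2.2 lists among the secondary endpoints "Predictive value of genomic events in determining mTOR inhibitor efficacy" and "Predictive value of protein biomarkers (pTEN, AKT, pSRB, LKB1) in determining mTOR inhibitor efficacy". Section 4.2.2 says how they are reported: "The clinical benefit rate at 6 months will be described with its 95% confidence interval according to" two sets of markers, namely "the presence/absence of each studied genomic event" and "the expression levels of each studied proteomic biomarker". Section 4.1.2 groups all five proteins under one immunohistochemistry study: "positive tumor markers (P4EBP1, PTEN, pAKT, pS6RB, LKB1) will be presented". The marker names below follow section 4.1.2.

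**The concern.** Where an outcome is set by judgement, masking keeps the judgement independent of the variable it will be compared with. Rule (3) applies that principle to p4EBP1. The SAP uses a single CBR-6m variable for all its marker work, so a value decided under rule (3) also enters the description by every genomic event and by PTEN, pAKT, pS6RB and LKB1. A reviewer could comply with the SAP to the letter while holding those results. Since rule (3) has no decision criterion, masking is its only stated safeguard, and for the secondary markers that safeguard is not written down.

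At stake is the credibility of the secondary estimates of CBR-6m by marker status. An outcome assigned with the marker in view cannot easily be made blind afterwards.

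**Working it through.** **Figures in the plan.** The SAP attaches no figure to rule (3). The design figure in section 3.1 is 80% power with 60 patients per p4EBP1 group, two-sided 0.05 and an odds ratio of 2.8. With p̄ the mean of p1 and p2 and n = 60,

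power = Φ{ (p2 − p1 − 1.96·√[2p̄(1−p̄)/n]) / √[p1(1−p1)/n + p2(1−p2)/n] }.

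This gives 78.4% for 30% vs 54.5%, 79.4% for 35% vs 60.1% and 79.4% for 40% vs 65.1%. The stated 80% is reproduced to within 2 points, and nothing in this point changes it.

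**Who reaches rule (3).**
- Rule (1) sets no for any progression documented up to 7 months.
- Rule (2) then sets yes for any complete response, partial response or stable disease recorded at 5 months or later. It has no upper time limit, so a patient with no scan between 5 and 7 months but stable disease at 8 months is already a yes.
- What remains for judgement is mainly (a) patients whose last evaluation, non-progressive, came before 5 months, and (b) patients with no evaluation before 5 months who are progressive after 7 months.
- Evaluability criterion 3 (sections 3.3 and 4.2.1) asks for a tumour evaluation 6 months after initiation. Read plainly, it removes group (a) from the efficacy population. It need not remove group (b).

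**Mask against use of the outcome.**
- p4EBP1: masked by name in rule (3); CBR-6m compared by chi-square test (section 4.2.1).
- PTEN, pAKT, pS6RB, LKB1: not named in rule (3); CBR-6m described with 95% confidence intervals (section 4.2.2).
- Genomic events: not named in rule (3); CBR-6m described with 95% confidence intervals (section 4.2.2).

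No other section masks the reviewers to the last two sets.

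**Size.** Suppose a share f of each marker group is decided by review, and that for otherwise similar patients the reviewers say yes at rate r without the marker and r + d with it. Then

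observed difference = true difference + f·[(r + d) − r] = true difference + f·d.

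The SAP gives neither f nor d. Over a range that is purely assumed:
- f = 5%: 1 point at d = 0.2 and 2.5 points at d = 0.5
- f = 10%: 2 points at d = 0.2 and 5 points at d = 0.5
- f = 20%: 4 points at d = 0.2 and 10 points at d = 0.5

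The list shows only that the effect scales with the number of reviewed cases and vanishes without them. It is not an estimate for this trial.

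**The case against.** The strongest reply is that the SAP does not say the reviewers are blinded to p4EBP1 and to nothing else. It places these decisions inside a blind review and then names p4EBP1. What the reviewers receive is an operational matter that a protocol or data-review document, not available here, may settle. It is fair that the SAP nowhere says reviewers will see other markers, and a reader should not infer that they do. What stands is that the SAP names one marker, leaves the general term undefined, and uses the outcome for many markers.

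Four stronger readings are tempting and are not supported.
- *The primary analysis is compromised.* Its masking is explicit. Leakage through other markers would require them to be correlated with p4EBP1, and the SAP gives no such correlation.
- *The bias runs in an expected direction.* The SAP states no hypothesised direction for any genomic event or for the four other proteins. The p4EBP1 cut-off itself is set without prior assumptions, and the other proteins follow the same approach.
- *CBR would shift by about 5 points.* One could reason that three changed outcomes in a group of 60 give 3/60 = 5 points. But 60 per group is the p4EBP1 split, which is the masked comparison; groups defined by a genomic event need not have that size, and the three changes are themselves assumed.
- *Every patient without a scan between 5 and 7 months goes to review.* Rule (2) settles many of them.

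It is also fair that section 4.2.2 plans description with confidence intervals for these markers against CBR-6m, with no test or decision rule. That lowers the weight but does not remove the gap: these estimates are how the predictive-value endpoints of section 2.2.2 are reported.

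**Conclusion.** The point holds for the secondary marker analyses only. Rule (3) assigns CBR-6m by judgement to patients left open by rules (1) and (2), its only named mask is p4EBP1, and the same variable is described by genomic events and by PTEN, pAKT, pS6RB and LKB1. As written, those estimates are not protected from reviewers knowing the marker. The primary comparison is not directly affected.

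No size can be given, because the SAP states no number of rule (3) cases. It is probably small: rules (1) and (2) leave a narrow remainder, evaluability criterion 3 may remove part of it, and bias arises only if reviewers both see a marker and decide differently by it. The conclusion assumes that no other trial document already extends the mask; if one does, the change merely records existing practice. It is a free improvement of low priority.

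**What to change.** In rule (3) of SAP section 4.2.1, replace the masking phrase with: *blinded to all biomarker data (p4EBP1, PTEN, pAKT, pS6RB, LKB1 and all genomic results)*. Add that the reviewed outcomes are locked before any biomarker data are merged with the clinical data, and report how many outcomes were decided by review.

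The cost is a line or two of SAP text and a review listing without biomarker columns. The same reviewers can do the work, and the sample size, endpoints and planned analyses stay as they are. The change has to be in place before the review takes place.

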2.2 Study endpoints

2.2.1 Primary endpoint

The primary endpoint of the trial is the predictive value of p4EBP1 in determining mTOR inhibitor efficacy, measured by the association between expression level of the biomarker (high vs low expression) and clinical benefit rate (CBR) 6 months after initiating EVE-EXE treatment. Clinical benefit at 6 months is defined as a complete or partial response or stable disease at 6 months after treatment initiation.

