3.1 Sample size

The primary endpoint of the study is the association between expression levels of p4EBP1 (high vs low expression) and clinical benefit after 6 months of EVE-EXE treatment (CBR-6m).

We plan to enroll 150 patients in the study in order to have a minimum of 120 patients evaluable for the primary endpoint (some patients may not be evaluable: their tumor samples may not being analyzable, patients may not have been treated with the treatment combination [EVE-EXE]...).

With a sample size of 120 patients (60 patients in each subgroup defined by low vs high expression), a twogroup chi-square test with a 0.05 two-sided significance level will have 80% power to detect an increase in CBR at 6 months corresponding to an odds ratio of 2.8 (from 30-40% in p4EBP1- group to 55-65% in p4EBP1+ group). We estimate that this benefit, compared with those observed in the TAMRAD study (Bachelot, 2012), will reflect a clinically meaningful predictive value of the studied biomarker.

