3.2 General statistical methods

Quantitative data will be described using the number of observations, mean, standard deviation, median, minimum and maximum values.

Qualitative variables will be described using frequency and percentage distributions. The number of missing data will be given, but will not be considered for the calculation of proportions.

All confidence intervals and statistical tests will be 2-sided and performed at a 5% level. P-values \geq 0.001 will be reported to 3 decimal places; p-values less than 0.001 will be reported as "<0.001".

Statistical analyses will be performed using SAS® software version 9.4.

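### No derivation rule makes death before 6 months a lack of clinical benefit; depending on the patient's scans, such a death becomes yes, blind review, Not Available or no value at all

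*SAP*

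**What the plan says.** SAP section 2.2.1 gives the definition: "Clinical benefit at 6 months is defined as a complete or partial response or stable disease at 6 months after treatment initiation". Section 4.2.1 then derives the variable by four rules taken in order:

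- Rule (1) sets *no* when progression is on a tumor evaluation form at or before 7 months. It is the only automatic *no*.
- Rule (2) sets *yes* when rule (1) does not apply and a form at or after 5 months shows response or stable disease.
- Rule (3) sends several situations to patient-by-patient review blinded to p4EBP1. They include patients whose last evaluation, within 5 months, was non-progressive.
- Rule (4) applies only where rule (3) does not, and assigns *Not Available*: "if the patient died before 7 months from other cause than clinical progression, then the variable 'clinical benefit rate at 6 months' will be set".

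On missing values, section 3.2 says: "The number of missing data will be given, but will not be considered for the calculation of proportions". Sections 3.3 and 4.2.1 also make a patient evaluable only with a tumor evaluation before treatment and another 6 months after its start (condition 3). For PFS, section 4.2.2 counts "the first documented disease progression or death from any cause" as the event.

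**The concern.** A patient who has died by month 6 is not in response and does not have stable disease at month 6. Under the SAP's own definition the outcome is known, and it is *no*. The rules instead let it depend on which forms exist, on the cause of death, and on a review that has no stated criterion for death.

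Leaving known failures out of the denominator, or scoring them as benefit, raises the overall CBR-6m. The primary question is the association with p4EBP1. If early deaths are unevenly spread between the high and low groups, the odds ratio is distorted as well, and the direction depends on the group in which the deaths fall.

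**Working it through.** **1. The plan's own figure.** Section 3.1 states: "With a sample size of 120 patients (60 patients in each subgroup defined by low vs high expression"), and "chi-square test with a 0.05 two-sided significance level will have 80% power to detect an increase in CBR at 6 months" for an "odds ratio of 2.8 (from 30-40% in p4EBP1- group to 55-65% in p4EBP1+ group"). With n per group and p̄ the mean of p1 and p2,

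z = [ |p2−p1|·√n − 1.96·√(2p̄(1−p̄)) ] / √(p1(1−p1)+p2(1−p2)).

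- 30% vs 55%, n=60: (0.25×7.746 − 1.96×0.699)/0.676 = 0.837, power 79.9%, OR 2.85.
- 40% vs 65%, n=60: (0.25×7.746 − 1.96×0.706)/0.684 = 0.808, power 79.0%, OR 2.79.

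The stated 80% reproduces and is not at issue.

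**2. The rules applied in order to constructed cases.**

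| Case | Result |
|---|---|
| Stable disease at 5.1 months, death at 5.6 months, no progression form | *yes*, rule (2) |
| Stable disease at month 3, toxicity death at month 4 | blind review, rule (3) |
| Stable disease at month 2, progression death at month 4, no progression form | blind review, rule (3) |
| Non-progression death at month 2, no post-baseline form | *Not Available*, rule (4); blind review if a patient never assessed counts as non-progressive under rule (3) |
| Progression death at month 2, no post-baseline form | no rule fits, so no value |
| Progression form at month 2, death at month 3 | *no*, rule (1), because of the form and not the death |

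All six patients are dead before month 6. Only the last is certain to be scored *no*.

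**3. Size for the overall rate.** The SAP gives no early-death rate, so 2 to 6 deaths in 120 (1.7% to 5%) is an assumption. With 56 benefits, counting deaths as *no* gives 56/120 = 46.7%. Dropping 2, 4 or 6 deaths gives 56/118 = 47.5%, 56/116 = 48.3% and 56/114 = 49.1%, a shift of 0.8 to 2.4 points.

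**4. Size for the comparison** (Pearson chi-square, no continuity correction; 4 deaths assumed, all dropped).

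| Low vs high | p |
|---|---|
| 22/60 vs 34/60, deaths counted as *no* | 0.028 |
| 22/56 vs 34/60, all 4 in low group | 0.061 |
| 22/57 vs 34/59, 3 low and 1 high | 0.040 |
| 22/58 vs 34/58, 2 and 2 | 0.026 |
| 22/60 vs 34/56, all 4 in high group | 0.010 |

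The starting table has OR (34/26)/(22/38) = 2.26, below the planned 2.8. At the planned rates, dropping 4 low-group deaths gives 18/56 vs 33/60, p=0.013; 21/56 vs 36/60, p=0.015; 24/56 vs 39/60, p=0.017.

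**5. A wider assumption.** Let a share d of a group die early and be dropped, so the observed rate is p/(1−d) on 60(1−d) patients. Take d=10%.

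| Planned rates | Deaths in both groups | Low group only | High group only |
|---|---|---|---|
| 30% vs 55% (OR 2.85) | OR 3.14 | OR 2.44, power 64.5% | OR 3.67, power 92.6% |
| 40% vs 65% (OR 2.79) | OR 3.25 | OR 2.32, power 59.8% | OR 3.90, power 94.4% |

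The higher power figures are not a gain: they come from an inflated odds ratio.

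**The case against.** Several stronger readings are tempting, and the SAP does not support them.

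- *That a patient who dies early can never be scored no.* Rule (1) does so whenever a progression form exists, and the blind review under rule (3) may do so. What is missing is a rule, or a criterion for the review, that makes death count.
- *That early non-progression deaths in general become Not Available.* Rule (4) opens by excluding cases that rule (3) catches, so deaths after an earlier non-progressive evaluation go to review. Rule (4) is left essentially with patients who had no such evaluation.
- *That the coding can be judged apart from the efficacy population.* It cannot. Read literally, condition 3 removes every case in the table that lacks a 6-month scan, and recoding rule (4) alone would then change nothing. Yet rules (3) and (4) expressly deal with patients without that scan, so the two parts of the SAP do not fit together.
- *That PFS contradicts the primary endpoint.* PFS is a different endpoint. Its handling of death shows only that one patient can be a PFS event and a *yes*, or a non-observation, for clinical benefit.
- *That a few deaths readily overturn the test.* The example crosses 0.05 only towards non-significance, and only with all 4 deaths in one group and a starting effect below the planned one.

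It is also fair to say that the *yes*-then-death case needs a death within about one month, that the tumor evaluation form is not shown and might capture clinical progression, and that the plan allows for loss: "We plan to enroll 150 patients in the study in order to have a minimum of 120 patients evaluable for the primary endpoint". That allowance of 1 − 120/150 = 20% protects precision. It does not correct the bias from losing patients because they failed.

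**Conclusion.** The point stands in this form: the rules leave the primary outcome wrong, undefined or uncriterioned for identifiable patients who die before month 6, and condition 3 removes most of them on a literal reading. The overall CBR-6m is biased upward, by about 1 to 2.5 points if 2 to 6 of 120 die early and are dropped. The bias in the high-versus-low comparison has no fixed direction and depends on how deaths split by p4EBP1 level. With 4 deaths dropped it matters to the test only in a near-threshold result with a lopsided split; at the planned effect it does not change significance. All sizes rest on assumed death counts, and on all such deaths being dropped although some would go to review.

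**What to change.** 1. Ahead of rules (2) to (4), set clinical benefit to *no* for death from any cause within 6 months of treatment initiation.
2. For deaths between 6 and 7 months, keep *yes* if there is a non-progressive evaluation at or after 5 months. Otherwise set *no* for progression deaths and send the rest to the blinded review, so that no death is left without a rule.
3. Let rule (1) also use clinical progression recorded as the cause of death or as the reason for treatment discontinuation. Items 2 and 3 meet in one case: a progression death between 6 and 7 months after a non-progressive scan at or after 5 months. The SAP should state which takes priority. Taking rule (1) first would match how it already treats a progression form at 6.5 months.
4. Amend condition 3 in sections 3.3 and 4.2.1 so that patients scored *no* by progression or death are evaluable without a 6-month scan. Without this, items 1 to 3 may have no effect.
5. Keep the present *Not Available* coding as a sensitivity analysis.

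The cost is SAP wording, a few lines of derivation code and a slightly lower stated CBR-6m. Cause of death (section 4.2.2) and reason for discontinuation (section 4.1.3) are already to be reported.
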